culprit lesions.²² The combination of stenosis + atheroma burden + luminal area produced an odds ratio of 3.99 (95% CI: 1.74-9.13, p=0.001) for culprit plaque. The GLAGOV study showed that PCKS9 inhibition reduced the percent atheroma volume of coronary arteries over a 78 week treatment period.²³ With atheroma volume now established as a viable biomarker, vwMRI is the optimal test to monitor it and stenosis, both for ICAD and in other locations of the cerebrovasculature, such as the carotid arteries, cervical vertebral arteries, and aortic arch.

A.5. Impact

The result of this study will be a dataset that lays the foundation for a randomized controlled trial of Repatha in ICAD patients. The data collected in this study will allow us to optimize a future clinical trial designed to demonstrate a reduction in stroke risk, ultimately making more efficient and economical progress towards our ultimate research goal of preventing stroke with Repatha. While we are proposing future studies to reduce ICAD stroke risk, it should be noted that our study will also evaluate the potential for Repatha to decrease cerebrovasculature stenosis and plaque burden, which would be a compelling primary prevention indication.

B. Approach

B.1. Study Hypothesis

We hypothesize that inhibition of PCSK9 with Repatha in patients with moderate to severe intracranial atherosclerosis will reduce validated biomarkers of stroke risk (stenosis and percent atheroma volume). To answer our hypothesis, we propose a single arm study of Repatha in 150 patients with a prior history of ischemic stroke and ICAD causing at least 50% stenosis of a major intracranial artery in the Circle of Willis ("index artery").

B.2. Study Design

We will enroll 150 ICAD patients with a prior history of ischemic stroke. Patients will be enrolled at up to 8 medical centers in North America. All patients will receive Repatha for 78 weeks and will have an MRI before beginning study medication and a comparison MRI immediately after completing study medication.

B.3. Investigational Treatment

The investigational treatment is Repatha 140 mg administered subcutaneously with a single-dose pre-filled pen syringe every 2 weeks for a total of 39 treatments. Dose modification is not allowed.

B.3.a. Inclusion Criteria

- Adult patients, ≥ 18 years of age

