- History of ischemic stroke, defined as an episode of neurological dysfunction caused by focal cerebral, spinal, or retinal infarction (American Heart Association definition).
- Large vessel atherosclerosis of an intracranial artery in the circle of Willis with 50-99% stenosis by WASID criteria (percent stenosis = (1-[diameter stenosis/diameter normal]) x 100%) on MRA, CTA or DSA
 - Eligible arteries: vertebral (V4), basilar, PCA (P1, P2), MCA (M1, M2), tICA, ACA (A1)
- Current statin use or contraindication to statin
- Fasting LDL-C ≥ 70 mg/dL or LDL-C ≥ 60 mg/dL if lipoprotein (a) > 30 mg/dL; within a year of randomization and on the current statin medication/dose

B.3.b. Exclusion Criteria

- Gadolinium or PCSK9 inhibitor allergy
- Acute or chronic kidney disease with eGFR<30 ml/min/1.73m²
- Pacemaker or other MRI contraindications per American College of Radiology guidelines²⁴
- Inability to return for 78 week follow-up clinic visit and vwMRI

Pregnant at time of enrollment

B.4. Investigational New Drug Status

We will not require an IND. Repatha is indicated to reduce the risk of myocardial infarction, stroke, and coronary revascularization in adults with established cardiovascular disease; and as an adjunct to diet, alone or in combination with other lipid-lowering therapies (e.g., statins, ezetimibe), for treatment of adults with primary hyperlipidemia to reduce low-density lipoprotein cholesterol (LDL-C). Our patient population meets these criteria given 1) history of ischemic stroke and 2) presence of moderate to severe ICAD.

B.5. Patient Recruitment

Patients will be approached first by a member of their clinical care team in order to gain permission for a study member to approach to discuss the study in detail. Only co-investigators or study coordinators on this study will consent patients. Standard consenting procedures will be followed, including giving patients and family members adequate time to discuss the study with the study team and amongst themselves prior to consenting. A full, written, IRB- approved Informed Consent document will be provided to the patient (or representative) for signature after the patient or patient's representative has had time to read it and ask questions. A copy will be given to the patient for his/her records. Proxy consent by legally authorized representatives will be allowed in the case of post-stroke aphasia or other cognitive disability, in order to not bias study entry by stroke severity.

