All drug compliance records will be kept current and will be made available for inspection by regulatory agency inspectors. Study drug will be given to patient at the baseline visit, and preferably at 6 month intervals thereafter. Instructions for shipping study drug to patients are provided in the appendix.

B.9. Study Timeline

There are two in-person study visits (baseline and 78 week follow-up) when patients will undergo vwMRI, approximately 60 minutes long, with a simultaneous clinical evaluation by a study investigator physician and blood draw. Every 2-4 months, the study coordinator will determine medication adherence, adverse events, or patient-reported recurrent stroke (see **Figure 1**).

	Screen/ Baseline	Day 1	Day 60	Day 120	Day 180	Day 240	Day 320	Day 480	Day 546
Informed Consent	Х								
Medical History/Current medications	х		х	х	х	Х	х	х	х
Vitals	Х								Х
Review CTA or MRA ¹	х								
Vessel wall MRI		Х							Х
Pregnancy test	Х								
Creatinine	Х								Х
Lipid panel	Х								Х
Lipoprotein (a)	Х								Х
Apolipoprotein B	Х								Х
Physical exam	Х								Х
Neurological exam	Х								х
NIHSS	Х								Х
Modified Rankin Scale	х								Х
Stroke adjudication			Х	Х	Х	Х	Х	Х	Х
Adverse event determination			х	Х	х	Х	х	х	х
Serious adverse events			Х	Х	Х	Х	Х	Х	Х

Figure 1: Schedule of Activities

1. To confirm ICAD of a major intracranial artery

B.10. Study Duration

- Estimated duration of research (study start to final study deliverable): 2 Years / 6 Months
- Estimated duration of first patient enrolled to last patient out: 2 Year / 0 Months
- Estimated duration for Amgen to supply study drug: 2 Year / 0 Months

C. Study Endpoints

C.1. Primary Endpoints

The primary endpoints are nominal change in the stenosis and percent atheroma volume (PAV) of cerebrovasculture arteries from baseline to week 78. We will use measure stenosis and PAV on vessel wall MRI (vwMRI), which evaluates all arteries from the aortic arch to the distal intracranial vasculature in a single scan. The primary endpoints will be analyzed for both: 1) all intra- or extracranial arteries that have at least 25% stenosis, and 2) seperately for the intracranial arteries. Stenosis and PAV will be measured using standard methodology.

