C.1.a. Primary endpoint measurement: All vwMRIs are on a 3T scanner with a 20- or 32-channel head coil and gadolinium. The field of view is from the aorta to the top of the skull. Sequences include the following for Siemens scanners and equivalents for Phillips and GE:

Sequence	3D ToF	DWI	3D FLAIR	3D MPRAGE	PD SPACE DANTE	3D SWI	T1 SPACE DANTE	T2 SPACE DANTE
Contrast (gadolinium)	Pre	Pre	Pre	Pre	Pre	Pre	Pre/Post	Post

DANTE = Delay Alternating with Nutation for Tailored Excitation (for blood suppression); DWI = Diffusion Weighted Imaging (Tensor technique); GRE = Gradient Recalled Echo; MPRAGE = Magnetization Prepared Rapid Acquisition Gradient recalled Echo; PD = proton density; SPACE = Sampling Perfection with Application optimized Contrasts using different flip angle Evolution; SWI = susceptibility weighted imaging (with quantitative susceptibility mapping); ToF = Time-of-Flight

At the completion of patient enrollment, two neuroradiologists will examine all vwMRIs in three separate viewing sessions to prevent viewer fatigue. They will be given a rater sheet directing them to record findings in the brain and all major vessels of the cerebrovasculature, including:

- a) Stenosis: will be identified by the luminal imaging component of the vwMRI protocol (MR angiography of the head and neck). Stenosis will documented on the NIH Stroke CDE "Vessel Imaging Angiography"²⁵ for all cerebrovasculature vessels from the aorta to distal intracranial vessels. Any vessel with >25% stenosis qualifies for computation of this composite outcome.
- b) Percent atheroma volume (PAV): We will use MRI-PlaqueView (VPDiagnostics, Seattle, WA) to measure PAV in the aortic arch, cervical carotid, cervical vertebral and all major intracranial arteries. MRI-PlaqueView is a powerful application that allows identification of (a) vessel lumen and outer wall (OW), (b) atheroma (both calcified and lipid rich). PAV is measured on the cross-sectional slice with the highest % stenosis. PAV = Σ(OWarea Lumenarea)/ΣOWarea × 1

C.2. Secondary endpoint 1

Secondary endpoint 1 is post-contrast plaque enhancement for intracranial arteries and intraplaque hemorrhage for the cartotid artery, which are determined by two experienced neuroradiologist raters. If there is disagreement, then a third rater serves as a tie-breaker. The signal intensity characteristics of both endpoints have been standardized in prior literature.

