We will fit a mixed effects linear regression model, specifically a LOESS smoothing curve, to change in stenosis/PAV and on-treatment LDL-C, HDL-C, and lipoprotein(a). We will also use a multivariable linear regression model with the outcome of the primary endpoints, adjusted for covariates that could be confounders such as age, gender, smoking, statin use/dose and relevant medical comorbidities. The primary endpoints will also be compared to an assumed value of 0% change in stenosis and PAV that would correspond to optimal medical management without a PCSK9 inhibitor. Although, some studies have suggested statin therapy can reduce carotid atherosclerosis, no such effect is known for ICAD. For this analysis, we will use linear mixed effects model to detect differences in the stenosis and PAV endpoints between patients taking Repatha or the presumed historical control values of 0% change. For the secondary endpoints, we will use logistic and linear regression depending on the nature of the variable and use the primary predictors of on-treatment LDL-C, HDL-C, and lipoprotein(a). For the exploratory endpoint of recurrent stroke, we will use the above mentioned methods as well as a Cox proportional hazards model for the endpoint of recurrent stroke with the observed rate in this study compared to controls matched according to degree to stenosis of the index artery. Due to differences in arterial structure and flow dynamics, there may be a more significant plaque reduction in certain intracranial vessels. We anticipate subgroup analyses, for example comparing change in stenosis or PAV in the middle cerebral artery versus the vertebral artery.

D.2. Power Analysis

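### No rule covers an artery stented, dilated or operated on between the two scans, so a procedure's opening of the lumen can count as regression on Repatha in both primary endpoints.

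*Combined protocol and SAP*

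**What the plan says.** C.1 defines the outcome: "The primary endpoints are nominal change in the stenosis and percent atheroma volume (PAV) of cerebrovasculture arteries from baseline to week 78". It is analysed in two artery sets. The first is "all intra- or extracranial arteries that have at least 25% stenosis"; the second is the intracranial arteries taken separately. C.1.a repeats the entry rule for the stenosis measurement: "Any vessel with >25% stenosis qualifies for computation of this composite outcome". Neither section says at which scan the threshold applies. For the second endpoint, C.1.a says "PAV is measured on the cross-sectional slice with the highest % stenosis".

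Under B.3.a, every patient has had an ischaemic stroke and has "Large vessel atherosclerosis of an intracranial artery in the circle of Willis with 50-99% stenosis by WASID criteria". The only exclusion in B.3.b that touches on implants is "Pacemaker or other MRI contraindications per American College of Radiology guidelines". B.2 fixes the scan times: patients "will have an MRI before beginning study medication and a comparison MRI immediately after completing study medication".

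D.1 gives the comparison: "The primary endpoints will also be compared to an assumed value of 0% change in stenosis and PAV". The covariates it names as examples are age, gender, smoking, statin use and dose, and comorbidities. Revascularisation is not among them. B.6 allows the investigator to withdraw a patient, but that power is discretionary, acts on the patient rather than the artery, and does not name procedures. D.3 deals only with patients who do not return.

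**The concern.** A revascularisation between the scans is foreseeable. The patients have symptomatic disease with a tight intracranial stenosis, the first artery set adds the extracranial vessels, follow-up lasts 78 weeks, and the protocol's own reference list includes trials of stenting and endarterectomy for carotid disease and of stenting for intracranial stenosis. B.6 also says that unnecessary withdrawals will be avoided, so such a patient would normally reach the second scan.

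The effect of a procedure on the lumen is far larger than the drug effect the study is built to find, which D.2 puts at 1% for PAV. A control arm would carry some of the same procedures and offset them. A fixed reference of 0% offsets nothing. Because PAV is wall area divided by outer-wall area, opening the lumen can move it as well as stenosis. Arteries chosen for a procedure may also be those that were getting worse, so a failure of medical treatment could be recorded as one of the best responses.

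**Working it through.** **Plan's own figures (D.2).** Inputs: 150 patients, 4 sites each, SD 4% for PAV, two-sided 0.05, 80% power, 25-30% withdrawal. With effective n = 4 × 150 / (1 + 3 × ICC), the smallest detectable change is (1.960 + 0.842) × 4 / √(effective n). The plan's 0.51% is reproduced at an ICC of about 0.08, which the plan does not state: effective n is about 483, and 2.802 × 4 / √483 = 0.51. Power above 80% for a 1% reduction is also reproduced; even at one observation per patient it is 86.5%. Both are PAV figures. The plan gives no SD and no detectable change for stenosis.

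**Arteries available.** After 25-30% withdrawal, 105 to 112 patients complete. At 4 arteries each that is 420 to about 450, and I use 435 as the midpoint. For the intracranial set I assume one artery per patient, about 110.

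**Assumptions.** The documents give neither a procedure rate nor its effect. I assume a fall of 50 to 60 points in stenosis per treated artery (for example, 70% to 10%) and no drug effect.

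**Shift in mean stenosis** = −(fall) × k / N, for k treated arteries out of N.
- One procedure, 60 points: −60/435 = −0.14.
- Four procedures: −50 × 4/420 = −0.48, and −60 × 4/435 = −0.55.
- One procedure in the intracranial set: −60/110 = −0.55.

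**Is that enough for a significant test?** The procedures also widen the SD. With p = k/N, SD = √(16 + fall² × p(1 − p)) and SE = SD/√N. This borrows the PAV SD of 4 for stenosis and treats arteries as independent. For a 60-point fall:

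| Treated | Mean shift | SD | SE | z | two-sided p |
|---|---|---|---|---|---|
| 4 of 435 | −0.55 | 6.99 | 0.335 | −1.65 | 0.10 |
| 5 of 435 | −0.69 | 7.54 | 0.362 | −1.91 | 0.06 |
| 6 of 435 | −0.83 | 8.06 | 0.386 | −2.14 | 0.03 |
| 1 of 110 | −0.55 | 6.96 | 0.664 | −0.82 | 0.41 |
| 4 of 110 | −2.18 | 11.92 | 1.137 | −1.92 | 0.055 |
| 5 of 110 | −2.73 | 13.12 | 1.251 | −2.18 | 0.03 |

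A 50-point fall gives the same thresholds: 6 of 435 (z = −2.03) and 5 of 110 (z = −2.14).

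**PAV.** If a procedure lowered an artery's PAV by 20 points, which is again an assumption, a shift of 0.51 would need 0.51/20 = 2.55% of arteries, about 11 of 420. The direction is less certain than for stenosis, because a procedure can enlarge the outer wall and can move the slice on which PAV is read.

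**Procedures before the baseline scan.** The outcome is week 78 minus baseline, and the baseline scan precedes the first dose. An earlier opening is in both values, so it contributes 0 to the change.

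**The case against.** Four things can fairly be said in the plan's defence.

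First, the text does not say that treated arteries stay in. It is silent, and if 25% were also required at week 78, an artery opened from 70% to 10% would drop out. A metal implant might also make the lumen unreadable. This stands as a limit on certainty. Applying the threshold at baseline is the natural reading, but it is a reading. The silence is also a reason to write the rule before the scans are read, since in an open single-arm study a later choice would be made with the results in view.

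Second, a reader might infer that arteries treated before enrolment also inflate the apparent benefit. The documents do not support that, because any earlier opening is already in the baseline value; re-narrowing afterwards would count against the drug. Whether a previously treated artery with residual stenosis still measures native plaque is a separate validity question and does not produce this regression.

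Third, a reader might infer that a few procedures would be enough for a positive trial, because a shift of about 0.5 matches the 0.51% in D.2. That comparison fails. The 0.51% belongs to PAV, and the same procedures inflate the SD, so four of 435 give p of about 0.10. With no procedure rate in the documents, how often the necessary number would occur is unknown.

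Fourth, procedures would not go wholly unrecorded. Figure 1 collects medical history at every contact from Day 60 to Day 546, with adverse-event and serious adverse-event rows alongside. What is missing is a field for the artery and date, and an analysis rule that uses it.

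**Conclusion.** The gap is real and lies in the definition of the primary endpoints. On the natural reading, an artery opened between the scans is scored as regression and tested against a fixed 0% with nothing to offset it. Under an assumed 50 to 60 point fall, about 1% of arteries shifts mean stenosis by about 0.5 points. Nominal significance with no drug effect needs about 6 of 435 arteries overall or 5 of 110 intracranial ones. Those two counts rest on the borrowed PAV SD and on independent arteries. Smaller numbers would not produce a positive test alone, but they would bias the estimate towards benefit and widen its error, which could also hide a true effect. The point is confined to procedures between the two scans. It should be corrected before the scans are read.

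**What to change.** - In C.1 and C.1.a, state that the 25% threshold is applied at the baseline vwMRI.
- At the contacts already scheduled in Figure 1, record the artery and the date of any revascularisation.
- In D.1, state that a measurement taken after a procedure is not used as that artery's response. Omit that artery, but not the patient, from the main analysis of both endpoints.
- Add a sensitivity analysis that scores such an artery as progression, because treated arteries may be those that were worsening. Fix the score to be used in advance.

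The cost is a few lines of text, one form field, and a small number of arteries lost from the main analysis. Omission alone may still favour the drug by removing probable failures; the sensitivity analysis is there to show how much that matters. The rule concerns analysis only and changes nothing in patient care.

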
C.2.a. Secondary endpoint 1 measurement:

a) ICAD post-contrast plaque enhancement (PPE): is a dichotomous variable evaluated on the T1 pre- and post-gadolinium sequences, with multiplanar reconstruction so the ICAD can be seen in cross section.²⁶ PPE is defined by placing a region-of-interest over areas of gadolinium enhancement in ICAD to evaluate if it is equal to or exceeds the signal intensity of the pituitary infundibulum, as previously described.²⁷

- b) Carotid intraplaque hemorrhage (IPH): MPRAGE positive plaque is defined as voxels with at least 2-fold signal intensity compared to sternocleidomastoid muscle as previously described. MPRAGE positive plaques can be reliably identified. Kappa values for inter- and intra-rater reliability for detection of MPRAGE positive plaque were 0.806 and 0.818 respectively (very good agreement).^{28,29}
- c) MRA Flow Dynamics (**MFD**): We will measure MFD using accepted quantitative MRA methodology. The VERiTAS study provided prospective confirmation of the importance of MFD as a biomarker of stroke risk for patients with ICAD. Given that MFD can easily be measured in our vwMRI protocol, we will acquire the data required for its quantification.

C.3. Secondary endpoint 2

To better understand the mechanism of Repatha's effect on intra- and extracranial atherosclerosis, we will measure the endpoint of change in cholesterol markers [LDL-C, HDL-C, lipoprotein (a), apolipoprotein B, and triglyceride level]. The change in cholesterol markers will be correlated with the primary and secondary study endpoints on vwMRI. Cholesterol values will be measured at the baseline and comparison MRIs, which are 78 weeks apart. If standard of care lab values are available within 30 days of the study visit, they can be used in place of the study lab value. An additional exploratory outcome that we will measure is the composite endpoint of "recurrent stroke," which encompasses new patient-reported symptomatic ischemic stroke, transient ischemic attack, or asymptomatic strokes that emerge between MRIs.

C.3.a. Secondary endpoint 2 measurement:

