- a) At both study MRIs, the study coordinator may collect two blood samples. Standard of care lab values can be used in place of these tests, if the values are from within 30 days of the study visit. If standard of care labs are not available, then the following samples will be tested. One sample may be tested with an i-STAT for creatinine levels prior to the MRI and, in women of child-bearing age who are not on birth control, a bHCG should be tested. The second sample may be sent for testing of LDL-C, HDL-C, triglycerides, apolipoprotein B, and lipoprotein (a), biomarkers of cardiovascular disease risk.
- b) At both study visits (baseline vwMRI and follow-up vwMRI), a physician will assess patients and their medical records for stroke. The physician will also have access to the data from the neuroradiologist raters. The endpoint of stroke is defined for all arterial distributions in the cerebrovasculature.

C.4. Data Collection and Management

Baseline and follow-up patient data are written on a case report form and then entered into a REDCap case report form (**eCRF**) based on the NIH Stroke Common Data Elements (CDE). We will also complete CRFs based on the "Demographics," "Health History," "Prior Health Status," and "Drugs" forms,²⁵ and utilize the SNOMED coding system for comorbidities.³⁰ All data analysis is conducted with Stata.

D. Methodology

D.1. Statistical methods

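### C.1.a sets no masking to time point and no reading order for the vwMRI reads behind a single-arm change endpoint, and it times the reading before the last week-78 scans can exist

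*Combined protocol and SAP*

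**What the plan says.** The study has one arm of 150 patients. B.2 gives each patient one vessel wall MRI before treatment and "a comparison MRI immediately after completing study medication". C.1 defines the outcome: "The primary endpoints are nominal change in the stenosis and percent atheroma volume (PAV) of cerebrovasculture arteries from baseline to week 78". D.1 includes a comparison of these changes with an assumed 0% change, standing for medical management without a PCSK9 inhibitor.

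C.1.a describes how the scans are read: "At the completion of patient enrollment, two neuroradiologists will examine all vwMRIs in three separate viewing sessions to prevent viewer fatigue". The readers complete a rater sheet. For PAV, C.1.a adds that "PAV is measured on the cross-sectional slice with the highest % stenosis". C.1 otherwise says only that the measures follow standard methods. The third-rater tie-break in C.2 belongs to secondary endpoint 1.

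Nothing in the text reviewed masks the readers to time point, removes dates or clinical data, sets a reading order, or says how a patient's two scans are placed in the three sessions.

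On timing, Figure 1 puts the follow-up scan at Day 546. B.10 gives: "Estimated duration of first patient enrolled to last patient out: 2 Year / 0 Months".

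**The concern.** Every follow-up scan is a post-treatment scan, so a reader who can tell which scan is which knows which one is expected to look better. With a control arm, a reading shift shared by both arms would largely cancel. Here the comparator is a fixed number, so any such shift goes straight into the estimated change. The planned effect is small (a 1% reduction in PAV), and PAV depends on which slice the reader takes as the most stenotic.

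The stated timing adds to the problem. Taken literally, it would have baseline scans read in one campaign and most or all follow-up scans read later. That reveals time point and confounds any drift in reading with change over time.

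**Working it through.** **1. Can the reading happen when stated?**

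Inputs: follow-up scan at Day 546 (Figure 1); an estimated 24 months, about 730 days, from first patient enrolled to last patient out (B.10).

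- Whatever the enrolment rate, the last enrolled patient's follow-up scan falls 78 weeks after that patient starts treatment. It cannot exist when enrolment completes.
- If B.10's estimate holds, enrolment closes by about 730 − 546 = Day 184. The first patient's follow-up scan is then still 546 − 184 = 362 days away, so almost no week-78 scans would exist.
- The second step rests on an estimate. Replacement of withdrawn patients (B.7) or extra enrolment (D.3) could lengthen enrolment. The first step does not depend on it.

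**2. The plan's own precision for PAV**

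Inputs from D.2: 150 patients, 4 sites each, SD 4%, two-sided 0.05, and a minimum detectable effect of 0.51% at 80% power. D.2 states no intra-class correlation (ICC).

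- Effective n = 150 × 4 / (1 + 3 × ICC); SE = 4 / √(effective n); detectable effect = (1.960 + 0.842) × SE.
- ICC 0: SE = 4/√600 = 0.163, detectable effect 0.457%.
- ICC 1: SE = 4/√150 = 0.327, detectable effect 0.915%.
- Working back from 0.51%: SE = 0.51/2.802 = 0.182; effective n = (4/0.182)² ≈ 483; design effect = 600/483 ≈ 1.24; ICC ≈ 0.24/3 ≈ 0.08.

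The 0.51% therefore reproduces with an ICC of about 0.081. D.2's power above 80% for a 1% reduction reproduces at any ICC from 0 to 1; it is 86.5% at ICC 1.

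**3. What a reading shift would do (illustration)**

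The documents give no size for a reader shift, so the shift *b* is an assumption and is varied. With no true change, the chance of a significant result is

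P = Φ(b/SE − 1.96) + Φ(−b/SE − 1.96).

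For b = 0.25 and SE = 0.182: b/SE = 1.374, so P = Φ(−0.586) + Φ(−3.334) ≈ 0.279.

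| Assumed shift (PAV points) | SE 0.182 (ICC ≈ 0.081, implied by 0.51%) | SE 0.258 (ICC 0.5) | SE 0.327 (ICC 1) |
|---|---|---|---|
| 0 | 5% | 5% | 5% |
| 0.10 | 8.5% | 6.7% | 6.1% |
| 0.25 | 27.9% | 16.2% | 11.9% |
| 0.50 | 78.4% | 49.1% | 33.4% |

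D.3 expects 25-30% not to complete, which leaves about 112 to 105 patients. At the implied ICC the three non-zero shifts then give 7.6%, 22.1% and 66.0% (n = 112) or 7.5%, 21.0% and 63.2% (n = 105).

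The same illustration cannot be made for stenosis, because the plan gives no SD for it.

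**The case against.** **The timing is only loose wording.** The sentence covers all vwMRIs and the endpoint needs week-78 scans, so read as a whole it can only be carried out after follow-up. This is fair. A reader might infer that the plan intends to read baselines first and follow-ups later; the documents do not support that intention. The timing calls for a wording correction. The missing masking and order remain under either reading.

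**The size is invented.** The shift is assumed, and it drives the result more than the ICC does. This stands. A reader might take 28% as the trial's false-positive rate, but nothing in the documents gives the size or direction of any reader shift, or shows that one will occur.

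**The study is preparatory.** A.5 presents it as the foundation for a randomised trial, and the 0% comparison is one of several D.1 analyses. This also stands and limits the severity. A shift uniform across patients would leave the slopes on lipid values unchanged. One that varied with something correlated with lipids could alter them, so those analyses are neither clearly affected nor clearly safe.

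**The stroke assessment.** C.3.a(b) says: "The physician will also have access to the data from the neuroradiologist raters". A reader might infer that this compromises the readers' masking. It does not: the data run from the readers to the physician, and recurrent stroke is exploratory. Finding "asymptomatic strokes that emerge between MRIs" needs both scans, so access after the endpoint read would fit the text. No change is asked for there.

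**Conclusion.** The point holds in limited form. The plan tests a single-arm change against a fixed 0% and does not protect that change from a reading difference tied to time point. Its one timing statement cannot be followed as written.

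How much this matters depends on the assumed shift. At the SE implied by D.2, a shift of a tenth of the planned 1% effect barely moves the error rate (8.5%), a quarter gives about 28%, and a half about 78%. At ICC 1 the figures are about 6%, 12% and 33%. These rest on a normal approximation, SD 4%, four sites per patient, 150 patients and no true change. They show sensitivity and do not predict bias.

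The amendment should be made before any endpoint reading starts. It gives no reason to change the design or sample size.

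**What to change.** Amend C.1.a along these lines:

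> Endpoint reading begins after the last week-78 vwMRI has been acquired. Dates, identifiers and time point are removed from the images. Readers have no access to clinical or lipid data. Scans are read in an order that is random with respect to time point.

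C.1.a should also say how a patient's two scans are placed in the three sessions. Reading both masked scans in the same session is one reasonable option: it keeps between-session variation out of the change and helps the readers match the site. Reading them apart, to limit recall, is another. The documents do not settle this, and the point does not depend on it.

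The cost is image de-identification and a random list, with no extra scans, reads or readers. Reading starts later than the literal text says. B.10 also gives: "Estimated duration of research (study start to final study deliverable): 2 Years / 6 Months". Against 24 months from first patient enrolled to last patient out, this leaves up to 30 − 24 = 6 months. That margin must cover start-up, reading, analysis and the final deliverable, so the reading time should be planned within it.
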